7.6. Pharmacokinetics

Blood samples for PK analysis of TQ will be collected at the time points indicated in the Time and Events Table (Section 7.1). The Day 3 sample should be taken 24-96 hours after TQ dosing and a concurrent set of vital signs should also be obtained. Sample(s) of 1 mL blood will be collected (via venipuncture) into blood tubes and/or 70 µL blood (via finger or heel prick) will be collected into capillary tubes. Each sample will be centrifuged to produce plasma and the plasma transferred into a tube for shipping to a central laboratory for analysis. The actual date and time of each blood sample collection will be recorded. The timing and collection of PK samples may be altered and/or PK samples may be obtained at additional time points to ensure sufficient PK monitoring. In addition, concentrations of CQ will be determined. Details of the PK blood sample collection (both venipuncture and microsampling), processing, storage and shipping procedures are provided in the SRM.

Evaluation of correlation between venous and microsampling data will be made at each interim analysis. If microsampling data is deemed adequately representative of venous blood samples, any further PK sampling will switch predominantly to microsampling. However, up to two out of the four planned PK samples per subject may still be collected by both venous and microsampling methods. This will be as a back-up given the primary objective of this study is to adequately characterize the PK of TQ in the pediatric population. The PK data hence is of critical value. In the event that microsampling data is deemed an inadequate representation of venous samples, any further PK sampling will be only by venous sampling.

The sampling strategy of four PK samples per subject is designed to be sparse but adequately characterize the PK of TQ in the pediatric population. These four samples per subject will be reduced to two samples per subject at the earliest interim analysis once reliable characterization of TQ PK has been achieved.

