3. PLANNED ANALYSES

3.1. Interim Analyses

Up to two main interim analyses have been planned so that serial but sparse PK sampling (i.e., 4 PK timepoints) may be reduced at the earliest opportunity. The first interim analysis will take place after a total of at least 16 subjects in the main cohort have PK evaluable data or 12 months post study initiation, whichever comes first. The second interim analysis will take place after a total of at least 32 subjects in the main cohort have evaluable PK data or at 24 months post study initiation, whichever comes first. The second interim analysis will take place only if serial but sparse PK sampling is continued after the first interim analysis.

The interim analyses will be performed after the completion of the following sequential steps:

1. All required subjects (i.e. 16 or 32 subjects) have PK evaluable data as defined in the protocol (or 12/24 months post study initiation).
2. All required database cleaning activities have been completed and interim database release and database freeze has been declared by Data Management.

If it is found that due to insufficient number of children being enrolled in the lowest weight band(s) the prediction intervals are wider in that lowest weight band, then further serial (but sparse) sampling may be limited to the children being enrolled in the lowest weight band. The analyses will then be repeated after next set of 4 subjects and so on until the TQ PK for that weight band are adequately characterized and the 95% interval within the targeted 55-162 $\mu\text{g}\cdot\text{hr}/\text{mL}$.

See [Appendix 12](#) for details about the population pharmacokinetic analysis.

The correlation between TQ PK data from venous sampling and capillary microsampling will be evaluated. Based on the emerging data, if deemed appropriate, further PK sampling of TQ in pediatric subjects will be limited predominantly to capillary microsampling to reduce the PK sampling burden on this highly vulnerable population. Agreement will be evaluated based on correlation and Bland-Altman analyses. Further details will be documented in the TAF113577 Interim Analysis Charter.

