8.8. Evaluation of Microsampling

The relationship between venous blood sampling concentrations and capillary microsampling concentrations will be explored using the PK population.

A scatterplot comparing the venous blood plasma concentrations and the microsampling blood concentrations for all subjects, at all timepoints will be produced. In addition, the correlation between the methods will be calculated and presented in the same plot. The correlation will be calculated separately for each quartile, according to the concentration range observed.

To quantify the level of agreement between the blood sampling methods, a Bland-Altman plot will be produced [Bland, 1999]. The plot will display average concentration (x-axis) versus the concentration ratio (microsampling concentration/venous concentration) (y-axis). The following reference lines will be included in the plot

- Mean concentration ratio (bias)
- Mean concentration ratio \pm 5% (interim analysis 1 only)
- Mean concentration ratio \pm 15% (interim analysis 2 and SAC only)
- Limits of agreement calculated as: mean concentration ratio \pm 1.96 x SD

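### The microsampling Bland-Altman plot averages raw ratios, so its bias line is expected to sit above 1 and both limits of agreement too low even when the two methods agree

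*SAP*

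**What the plan says.** SAP 8.8 compares venous and capillary concentrations with a scatterplot, correlations and a Bland-Altman plot. For the last it says: "The plot will display average concentration (x-axis) versus the concentration ratio (microsampling concentration/venous concentration) (y-axis". The reference lines are:

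- the bias line, given as "Mean concentration ratio (bias";
- the mean ratio plus or minus "5% (interim analysis 1 only";
- the mean ratio plus or minus "15% (interim analysis 2 and SAC only";
- limits of agreement, given as "Limits of agreement calculated as: mean concentration ratio" plus or minus 1.96 times the SD.

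Neither a log transformation nor a geometric mean is mentioned, so the mean is read as arithmetic on the raw ratio.

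SAP 3.1 gives the purpose: "Agreement will be evaluated based on correlation and Bland-Altman analyses". Protocol 7.6 gives the consequence: "If microsampling data is deemed adequately representative of venous blood samples, any further PK sampling will switch predominantly to microsampling". If the microsampling data are judged inadequate, later sampling is venous only. No numerical criterion appears in either document. SAP 3.1 defers this: "Further details will be documented in the TAF113577 Interim Analysis Charter". The charter is not among the documents.

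**The concern.** A ratio of two positive measurements that both carry error is right-skewed. Its arithmetic mean is expected to exceed 1 even when neither method reads higher than the other, and this holds in both directions: microsampling/venous and venous/microsampling both average above 1. A bias statistic that makes each method appear to over-read the other is not a sound measure of bias. Limits placed symmetrically around that mean do not fit a skewed distribution either.

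The mean-ratio line is the only estimate of bias in SAP 8.8, because a correlation does not respond to a proportional difference. The 5% and 15% lines do not help, since they are drawn around the observed mean ratio and move with it. The plot could therefore suggest a small over-read by the capillary method that is not there, or offset a true under-read of similar size. The sampling method supplies the concentrations behind the primary AUC endpoint, so the comparison should be on a sound scale.

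**Working it through.** **Inputs.** The statistics are those of SAP 8.8. The documents give no SD of the ratio, no error for either method and no expected number of pairs, so there is no stated figure to reproduce. The error is an assumption: independent log-normal error of equal CV in each method, no relative bias, CV from 10% to 25%.

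**Formulas.**

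- Log-scale variance per method: ln(1 + CV²).
- SD of the log ratio: s = √(2 ln(1 + CV²)).
- Expected mean ratio: exp(s²/2) = 1 + CV². Inverting the ratio leaves s unchanged, so the result is the same in both directions.
- SD of the ratio: (1 + CV²) × √((1 + CV²)² − 1).
- Planned limits: mean ± 1.96 SD.
- Log-scale limits, back-transformed: exp(±1.96 s), around a geometric mean ratio of 1.
- Tail shares beyond the planned limits: normal probabilities of ln(limit)/s.

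**Worked case, CV 20%.**

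- s = √(2 ln 1.04) = 0.280.
- Mean = 1.04.
- SD = 1.04 × √(1.0816 − 1) = 0.297.
- Planned limits: 1.04 ± 1.96 × 0.297 = 0.458 to 1.622.
- Log-scale limits: exp(±1.96 × 0.280) = 0.578 to 1.731.
- Lower tail: ln(0.458)/0.280 = −2.79, or 0.3%. Upper tail: ln(1.622)/0.280 = 1.73, or 4.2%.

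**Range.**

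| CV per method | Expected mean ratio | Planned limits | Log-scale limits | Below / above planned limits |
|---|---|---|---|---|
| 10% | 1.010 | 0.729–1.291 | 0.758–1.319 | 1.3% / 3.5% |
| 15% | 1.0225 | 0.595–1.450 | 0.661–1.512 | 0.7% / 3.9% |
| 20% | 1.040 | 0.458–1.622 | 0.578–1.731 | 0.3% / 4.2% |
| 25% | 1.0625 | 0.315–1.810 | 0.505–1.979 | 0.05% / 4.4% |

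The log-scale limits leave 2.5% in each tail in every row. The planned limits leave 4.5% to 4.8% outside in total, so overall coverage is close to 95% throughout; what fails is the split.

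**Checks.** Simulating one million pairs with log-scale SD 0.10 per method and no bias gave a mean of 1.010 for microsampling/venous and 1.010 for venous/microsampling; the geometric mean was 1.000. Making both methods unbiased on the raw scale instead gave the same inflation. It disappeared only when the venous value was error-free and microsampling was unbiased on the raw scale.

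**High-end illustration.** The one log-scale error in the documents is the adult model residual of 0.2657 (Protocol Appendix 9, Table 7). It includes model misfit and is not a paired-sample error. Used as the log-scale SD per method, it gives an expected mean ratio of 1.073 and planned limits of 0.254 to 1.892, against 0.479 to 2.089 on the log scale.

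**The case against.** **No stated rule.** SAP 8.8 describes an exploration and lists reference lines on one plot. The judgement is left to what is deemed appropriate, with details in a charter that is not supplied. Protocol 7.6 also allows up to two of the four samples per subject to be taken by both methods after a switch. This stands: a reader might infer that these statistics decide the switch and could tip it wrongly, but the documents state no threshold on the mean ratio or the limits.

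**The 5% lines are not a bias margin.** A reader might infer that the artefact uses up a 5% tolerance. It cannot, because the lines follow the observed mean. The expected inflation would equal 5% only near a 22% error per method, and 15% only near 37%. The 5% lines also apply to the first interim only. The SAP already carries the doses revised after cohort 1 and cohort dates into 2019, so that interim was probably over when this version was written. This stands too, although the same centring is why the lines cannot show a bias.

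**The effect is small against noise.** The inflation is an expectation, not a feature of every plot. At CV 20% with 64 independent pairs (16 subjects, all four samples paired), the standard error of the mean ratio is 0.297/8 = 0.037, about the size of the 0.04 inflation. At a log-scale SD of 0.10, 71% of simulated means from 64 pairs exceeded 1. This limits the practical weight, but noise does not justify a statistic that is off in expectation when a better one costs almost nothing.

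**Size is assumed.** At a CV of 10 to 15% the inflation is only about 1 to 2%. That is correct.

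**Conclusion.** The point holds as a low-cost improvement. As specified, the bias line is inflated in expectation by CV² and both limits of agreement sit too low: +1.0% to +6.25% for an assumed CV of 10% to 25% per method, with the tails at 20% split 0.3% and 4.2% instead of 2.5% each. These sizes rest on equal, independent log-normal error with no true bias. The documents lend the log-normal form some support, since the adult model residual is on the log scale (Protocol Appendix 9), but they give no between-method error.

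Three stronger readings are not supported: that the plan contains a pass/fail rule that the artefact would trip, that the artefact consumes a 5% margin, and that the limits lose their 95% coverage. The planned AUC estimation method is unaffected.

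**What to change.** In SAP 8.8, calculate log(microsampling) − log(venous) for each paired sample. Report the back-transformed mean, which is the geometric mean ratio, as the bias, and exp(mean ± 1.96 SD) as the limits of agreement. Draw the 5% and 15% reference lines around a ratio of 1, so that a departure of the bias line from agreement can be seen.

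No new data are needed. The cost is a short SAP edit and a line of code for the paired log difference. The log concentration already specified (LNTQ) belongs to the population PK file, whose specification lists no venous/capillary identifier, so the pairing must be built in the programs for Figures 4.1 and 4.2. If comparability across deliverables is wanted, earlier interim plots would have to be re-run on the new scale.

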10.1. Appendix 1: Protocol Deviation Management and Definitions for Per Protocol Population

10.1.1. Exclusions from Per Protocol Population

No per protocol population has been defined for this study.

10.2. Appendix 2: Time & Events

10.2.1. Protocol Defined Time & Events

Protocol Activity	Visit Day									
	Screen & Treat	Follow-Up Period							Recurrence Visit ^a	Withdrawal Visit ^b
	Day 1 ^c	Day 3	day 8	Day 15	Day 29	Day 60	Day 90	Day 120	Recurrence	Withdrawal
Window		+2d	-/+2d	-/+3d	-/+5d	-/+10d	-/+10d	-/+10d		
Informed Consent Process	X									
Demographic Information	X									
Initial History Only ^d	X									
Physician Assess. Malaria Signs & Symptoms	X									
Inclusion/Exclusion Criteria	X									
Efficacy Assessments										
Parasitological Assessment (blood smear)	X		X		X	X	X	X	X	X
Plasmodium PCR genotyping	X								X	
Safety Assessments										
Review Concomitant Medications	X	X	X	X	X	X	X	X	X	X
Vital Signs ^{e,f}	X	X		X	X	X			X	X
Brief Physical Examination ^f	X	X	X		X	X	X	X	X	X
Adverse Events Assessment ^g	X	X	X	X	X	X	X	X	X	X
Serious Adverse Events ^h	X	X	X	X	X	X	X	X	X	X
G6PD (phenotyping) ⁱ	X									

Protocol Activity	Visit Day									
	Screen & Treat	Follow-Up Period							Recurrence Visit ^a	Withdrawal Visit ^b
	Day 1 ^c	Day 3	day 8	Day 15	Day 29	Day 60	Day 90	Day 120	Recurrence	Withdrawal
Window		+2d	-/+2d	-/+3d	-/+5d	-/+10d	-/+10d	-/+10d		
G6PD (genotyping)	X ^j									
Laboratory Assessments										
Hematology ^k	X	X	X							
Clinical Chemistry ^l	X		X							
Methemoglobin	X		X							
Pregnancy Test ^m	X				X	X	X		X	X
Pharmacokinetic Assessments										
Pharmacokinetic Sampling		X ⁿ		X ^o	X ^o	X			X	
Investigational Product										
Dispense Open Label tafenoquine	X									
Treatment Compliance Int. - Invest.	X									
IVRS Registration	X									

- a. Subjects who have a recurrence will continue to be monitored for safety and efficacy at all scheduled visits through day 120. Recurrence is defined by a positive blood smear with or without vivax malaria symptoms.
- b. If a subject withdraws, the site should offer to conduct safety assessments through Day 120.
- c. Visit Day 1 includes all screening procedures and treatment with tafenoquine.
- d. Includes medical, disease and therapy histories.
- e. Vital signs include height and weight (screening only), blood pressure, temperature, heart rate and respiratory rate.
- f. At Center^{PPD} Vital Signs and Brief Physical Examination will be performed at every visit.
- g. Adverse events are recorded from the time of the first dose of study medication.
- h. Serious adverse events are recorded from the time of consent in order to fulfil international regulatory requirements.
- i. G6PD phenotyping to be performed by quantitative spectrophotometric analysis. One or more G6PD rapid point of care tests may be performed at baseline (Day 1) only.
- j. A blood sample for G6PD genotyping will be collected only from subjects who experience a SAE due to hemoglobin decline. Subjects with hemoglobin decline should continue to attend all visits through Day 120 to monitor Hb status.
- k. Hematology includes hemoglobin, hematocrit, red blood cell/white blood cell/platelet counts, mean cell volume, white blood cell differential and reticulocyte count.
- l. Clinical Chemistry includes CPK, BUN, serum creatinine, total and indirect bilirubin and liver clinical chemistry.

CONFIDENTIAL

TAF113577

- m. Pregnancy testing is only for females of child-bearing potential. Use a urine pregnancy test that is routinely used at the site with a test sensitivity for human chorionic gonadotropin (hCG) level ≤ 25 mIU/mL.
- n. Day 3 PK sample must be taken 24-96 hours post TQ dose.
- o. Once full PK sampling has completed, remaining enrolled subjects will provide two PK samples at Day 15 and Day 29.

10.3. Appendix 3: Assessment Windows

10.3.1. Definitions of Assessment Windows for Analyses

Domain	Parameter (if applicable)	Target	Analysis Window		Analysis Timepoint
			Beginning Timepoint	Ending Timepoint	
Safety, PK, Efficacy	All	Day 1	Day -2	Day 1	Day 1
Safety, Efficacy	All except PK	Day 3	Day 3	Day 5	Day 3
Safety, PK, Efficacy	All	Day 8	Day 6	Day 10	Day 8
Safety, PK, Efficacy	All	Day 15	Day 12	Day 18	Day 15
Safety, PK, Efficacy	All	Day 29	Day 24	Day 34	Day 29
Safety, PK, Efficacy	All	Day 60	Day 50	Day 70	Day 60
Safety, PK, Efficacy	All	Day 90	Day 80	Day 100	Day 90
Safety, PK, Efficacy	All	Day 120	Day 110	Day 130	Day 120

For all data summarised by visit, the nominal visit description will be used. Unscheduled and withdrawal visit data will be slotted into a scheduled visit window, but the data will only be included in summaries and figures if no scheduled visit exists within the window. If there are multiple assessments within the same window which are not unscheduled visits, the earliest results will be used in the summaries. If only unscheduled visits are included in the same window, the earliest of these results will be used in summaries and figures.

For derivations of the maximum/minimum value/change post-baseline, then all data will be considered, regardless of whether or not it slotted to a scheduled window.

10.4. Appendix 4: Treatment States and Phases

10.4.1. Treatment States

Adverse events will be classified according to time of occurrence relative to the start of the study treatment. No other treatment states are required for this study.

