2.2. Brief Background

Tafenoquine has been shown to have an acceptable safety profile in the treatment and prevention of plasmodial infections in pre-clinical models and during Phase I, II and III clinical studies in >4000 subjects aged ≥16 years old.

All members of the 8-aminoquinoline class of drugs, including TQ and PQ, induce hemolysis in subjects with G6PD deficiency. G6PD is a housekeeping enzyme responsible for protection against oxidant stress. The effects of oxidant stress in subjects with G6PD deficiency are most apparent in red blood cells. Tafenoquine is thus being developed for treatment of patients with sufficient levels of G6PD enzyme activity.

Tafenoquine has a long half-life, and as such can be administered as a single oral dose. This is in contrast to PQ, which requires 14 days dosing. It must be determined if improved compliance with TQ could also lead to improved clinical outcomes. Tafenoquine should have no clinically significant side effects that will restrict its use as a first line agent in treatment of *P. vivax* malaria when used in combination with a G6PD test and recommended therapies to treat the blood stages of infection.

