6.9.1.2. Rescue Medication

Subjects requiring rescue medication will be given appropriate medication in accordance with site (local) or national treatment guidelines for *P. vivax* malaria or; e.g., *P. falciparum* malaria, whichever is applicable. Subjects offered rescue medication should be followed up for safety assessment through the Day 120 visit to ensure resolution of the malaria infection. Details of rescue medication including reason for the rescue medication offered (e.g., withdrawal from study, treatment failure) should be recorded in the eCRF.

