8.2.1.1. Adverse Events

Counting of Adverse Events (AEs) will be based on the number of subjects – not the number of AEs. For example, if a subject reports the same AE on three occasions within the relevant time interval, that AE will only be counted once. If a subject experiences the same AE (i.e. same preferred term (PT)) more than once, they are counted only once under the count for the preferred term. If a subject experiences more than one AE in a particular System Organ Class (SOC), they will only be included once in the count for the SOC, but will appear in the count for each appropriate preferred term within the SOC. Therefore, the sum of the numbers of subjects with each preferred term event within a SOC may exceed the total number of subjects with at least one event. For the summary of AEs by maximum intensity, subjects who experience the same event several times with different intensity will only be counted once with the maximum intensity.

Only treatment emergent AEs (TEAEs) will be presented as all subjects receive study medication on Study Day 1. TEAEs are defined as AEs with an onset date and time on or after that of the start of first dose of study medication (including CQ).

The recurrence of *P. vivax* malaria and any associated signs and symptoms are recorded as Disease Related Events (DREs) and will not be included in the AE data displays, but will be listed separately.

Adverse Events will be summarized by dose group and overall as specified below and in [Appendix 15: List of Data Displays](#), and presented in order of descending frequency. [Table 3](#) provides an overview of the planned analyses, with further details of data displays being presented in [Appendix 15: List of Data Displays](#).

Table 3 Overview of Planned Adverse Event Analyses

Endpoint / Parameter/ Display Type	Absolute		
	Summary		Individual
	T	F	L
Adverse Events (AEs)			
All AEs			Y ¹
All TEAEs by SOC	Y		
All TEAEs by PT	Y		
Drug-related TEAE by PT	Y		
TEAEs by maximum grade or intensity	Y		
Common (≥10% in any treatment group) TEAEs by PT	Y	Y ²	
Common (≥10% in any treatment group) Non-serious TEAEs by SOC and PT – number of subjects and occurrences	Y		
TEAEs by week and month of onset	Y		
Subject numbers for individual AEs			Y
Relationship between AE SOC, PTs and verbatim text			Y
All drug-related TEAEs by SOC and maximum grade or intensity ⁴	Y		
Serious and Other Significant AEs			
Fatal TEAEs by PT	Y		Y
Serious TEAEs ³	Y		Y

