10.6.3. Safety

Adverse Events

 • All AEs reported up to and including the Day 120 visit following enrolment of a subject into the study will be documented. • These will be recorded and coded using the current version of Medical Dictionary for Regulatory Activities (MedDRA). All terms applied will be reviewed by a GSK physician prior to database freeze. If any malaria related coded terms are considered to have lost useful information in the coding step (e.g., if a verbatim term of 'Plasmodium vivax malaria' is mapped to 'malaria'), he/she will recommend a study-specific code, which will be documented. • Treatment emergent AEs are defined as AEs with an onset date and time on or after that of the start of first dose of study medication (including CQ). • AEs with entirely missing or unknown start dates will be assumed to be treatment emergent for reporting. AEs where the start date is equal to that of study medication, but where the start time is unknown will also be assumed to be treatment emergent. AEs with missing end dates are not anticipated to affect reporting. • If the grade/intensity is missing for an AE, it will be considered severe/Grade 3 if an AE, or Grade 4 if an SAE and the subject is alive, or Grade 5 if an SAE and the subject dies (i.e. the highest intensity possible) for the summary of AEs by maximum intensity. • See Section 10.7.2 for more information on missing and partial dates. • Common AEs are those occurring in ≥10% of subjects in any treatment group. • The recurrence of malaria and any associated signs and symptoms are recorded as Disease Related Events (DREs) and will not be classified as AEs. • The GSK clinical team will review terms that qualify as potentially hematologically related.

Laboratory Parameters

 • If a laboratory value which is expected to have a numeric value for summary purposes, has a non-detectable level reported in the database, where the numeric value is missing, but typically a character value starting with '<x' or '>x' is present, the number of decimal places of x will be used to determine how much to add or subtract in order to impute the corresponding numeric

Laboratory Parameters

value.

- Example 1: 2 decimal place = '< x' becomes $x - 0.01$
- Example 2: 1 decimal place = '> x' becomes $x + 0.1$
- Example 3: 0 decimal places = '< x' becomes $x - 1$

Vital Signs – Mean Arterial Blood Pressure

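### Adverse events that start after rescue antimalarials are tabulated in the child's tafenoquine dose group, and the SAP has no flag to separate them

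*SAP*

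**What the plan says.** **Treatment states.** SAP 10.4.1 places adverse events relative to the start of study treatment and closes with "No other treatment states are required for this study". The treatment-emergent definition in SAP 8.2.1.1 has a starting point, the first dose, but no end point.

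**Collection and grouping.** SAP 10.6.3: "All AEs reported up to and including the Day 120 visit following enrolment of a subject into the study will be documented". SAP 8.2.1.1: "Adverse Events will be summarized by dose group and overall as specified below". The groups are the tafenoquine doses.

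**Follow-up after rescue.** Protocol 6.9.1.2: "Subjects offered rescue medication should be followed up for safety assessment through the Day 120 visit to ensure resolution of the malaria infection".

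**Laboratory extremes.** SAP 10.3.1: "For derivations of the maximum/minimum value/change post-baseline, then all data will be considered", whether or not the value falls in a visit window.

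**What is kept out.** SAP 8.2.1.1 lists malaria recurrence and its associated signs and symptoms separately as disease-related events (DREs), outside the adverse event displays.

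**Contrast with efficacy.** SAP 10.6.4 has an explicit rule for children who take another drug with antimalarial activity. No safety section has a counterpart.

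**The concern.** The study has one arm, so nothing but the data handling can separate an effect of tafenoquine from an effect of later rescue treatment or of the second illness. Gastrointestinal tolerability and hemoglobin drops are the named safety endpoints of interest (Protocol 3), and the final dose recommendation is to take safety into account (Protocol 9.4.1, SAP 7.1.1).

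The misattribution need not be even across dose groups. The adult model in Protocol 2.1.2 gives 52% recurrence-free at six months below an AUC of 56.4 µg·h/mL and 85% at or above it. A group with lower exposure would be expected to have more recurrences, more rescue and more post-rescue events, and could look less well tolerated because it was exposed to less drug.

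**Working it through.** The plan gives no figure that depends on this rule, so there is none to reproduce. The check sets the rules side by side and then gives a scale.

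**1. Which adverse events reach the tables.**
- An effect of a rescue drug is not a DRE under any section. With onset by Day 120 it is a treatment-emergent event in the tafenoquine dose group.
- For symptoms of the recurrence itself the text is mixed. Protocol 7.5.1.6 sends malaria and its associated signs and symptoms to the DRE page. The symptoms it names are pyrexia, chills, rigor and headache, and only with a positive slide at the time; with a negative slide they are adverse events. Protocol 7.2 also counts vomiting, nausea, abdominal pain and diarrhea among vivax symptoms. A site could record those on either page.

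**2. Which adverse event tables are affected.** Under SAP 10.4.1.1, Table 3.11 covers onset on Study Days 30 to 90 and Table 3.12 onset from Day 91, when rescue for a recurrence is most likely to have happened. Tables 3.1 (all events), 3.4 (drug-related) and 3.20 (potentially hematologically related) have no time limit. For Table 3.4 the SAP is also inconsistent: 8.2.1.1 counts an event as related only when marked Yes, while 10.4.1.1 also counts a missing answer.

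**3. Which laboratory displays are affected.**
- Scheduled hematology is on Days 1, 3 and 8, and chemistry on Days 1 and 8 (Protocol 7.5.6). Post-rescue values can come only from unscheduled tests, or from Days 3 and 8 if rescue is early, for example after two vomited doses (Protocol 6.1).
- These can enter extremes with no day limit: the maximum decline in Figure 3.3, the worst-case chemistry Table 3.24 and the maximum liver-test Figures 3.13 to 3.15.
- Tables 3.30 and 3.31 and Figure 3.9 stop at Day 10 or the Day 8 visit (SAP 8.4.2, 10.15.6, 10.15.7), and the Figure 3.2 nadir stops at the Day 8 visit.
- Table 3.27 does not carry hemoglobin. Abnormality tables use the F3 range only (SAP 8.4.1, note 1), and hemoglobin has only an F2 change criterion (SAP 10.8.1). A late hemoglobin fall goes to Listings 14 and 15.

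**4. Scale (assumption, not a trial estimate).** The adult figure at AUC 56.4 or above is 85% recurrence-free at six months (95% CI 80% to 90%), that is 10% to 20% recurrence. The endpoint here is at four months, so 5% is added as a lower case.
- Children rescued = 60 × p: 60 × 0.05 = 3; 60 × 0.10 = 6; 60 × 0.20 = 12.
- Chance of at least one at p = 5%: 1 − 0.95^60 = 0.954.
- Post-rescue share of child-days = p × (120 − rescue day)/120. Lowest, p = 5% and rescue at Day 90: 0.05 × 30/120 = 1.25%. Highest, p = 20% and rescue at Day 30: 0.20 × 90/120 = 15%.
- Small groups: the Protocol Appendix 9 weight distribution puts 5% in the 5–10 kg band, against 5 + 23 + 33 + 36 = 97% in the bands being enrolled. 60 × 0.05/0.97 = 3.1 children, so one event is about 32% of that band. In any group of 10 or fewer, one event reaches the SAP's 10% threshold for a common event.

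**The case against.** **Hemoglobin.** A reader might infer that the hemoglobin-fall results are contaminated. They largely are not, for the reasons in step 3. The quoted sentence in SAP 10.4.1 also follows one about adverse events, so it is not a laboratory rule; the laboratory route rests on SAP 10.3.1 alone.

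**Recurrence symptoms.** A reader might infer that every symptom of a second infection is counted against tafenoquine. The DRE rules divert associated signs and symptoms, and Protocol 12.3.1 excludes expected symptoms of the studied disease unless more severe than expected. What stands is the ambiguity over gastrointestinal symptoms and the absence of any rule for rescue-drug effects.

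**Hemolysis from rescue drugs.** Protocol 2.2 says: "All members of the 8-aminoquinoline class of drugs, including TQ and PQ, induce hemolysis in subjects with G6PD deficiency". That concerns deficient subjects, and enrollment requires G6PD activity of at least 70% of the site median. Rescue also follows local guidelines, so the drug is not specified. The sentence does not show that rescue would cause hemoglobin falls here.

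**Existing separation.** Events are split by onset period, causality assessment must consider concomitant therapy (Protocol 12.3.5), and Listing 23 carries concomitant medications. With a handful of rescued children, case-by-case reading is possible. This helps, but the onset tables do not separate rescued from unrescued children, and a reader would have to join listings by hand.

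**All data by design.** Counting everything to Day 120 after a single dose is a defensible, conservative choice in a descriptive study. That stands, and is why the all-events tables should remain the main display. The SAP does not state the choice or offer the complementary view.

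**Size.** In a group of 10, any one event moves the rate by 10 points. That shows sensitivity, not bias.

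**Conclusion.** The point holds for adverse events: those starting after rescue are tabulated as treatment-emergent in the tafenoquine dose group through Day 120, and nothing in the safety sections identifies them. It holds only narrowly for laboratory data.

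The size is minor to moderate. It rests on an assumed 5% to 20% recurrence (about 3 to 12 of 60 children) and on rescue between Days 30 and 90. The number of post-rescue events cannot be derived from the documents. The primary pharmacokinetic analysis is not affected by these tabulations.

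A reader might also infer that the late-onset tables exist to show delayed effects of a long half-life drug. The SAP gives no such purpose; they are simply where post-rescue events are most likely to fall.

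**What to change.** In SAP 10.4.1, add a derived flag for onset (or sampling) on or after the first antimalarial given for recurrence or rescue. Define it so that the initial chloroquine course, which may run past Day 1, does not trigger it; SAP 10.6.2 already makes that distinction.

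- Show the flag in adverse event Listing 8 and laboratory Listings 14 and 15.
- Add before-rescue versions of Tables 3.1, 3.4, 3.11, 3.12 and 3.20, keeping the all-events versions as the main display. For Tables 3.11 and 3.12, state how many children were still unrescued at the start of the period.
- Reconcile the two definitions of drug-related, since they feed Table 3.4.

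The inputs exist: rescue details and reason go in the eCRF (Protocol 6.9.1.2), administration dates are required (Protocol 6.9.1.1), and a clinician already classifies antimalarial concomitant medications for efficacy (SAP 10.6.4). The cost is SAP wording, one flag and a few extra outputs; no data are dropped. The flag will not catch recurrence symptoms that begin before the first rescue dose; those still depend on how the DRE rule is applied.
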